10.6.1.12. Handling of Overdose

In the context of a clinical study, an overdose is any dose which exceeds the daily dose that is defined in the clinical study protocol.

If an overdose on a study drug occurs in the course of the study, then the investigator or other site personnel shall inform the appropriate sponsor representatives immediately, or **no later than 24 hours** of when he or she becomes aware of it. The designated sponsor representative shall work with the investigator to ensure that all relevant information is provided to the sponsor or designee.

For overdoses associated with a SAE, the standard reporting timelines apply, see Section 10.6.1.9.

G1T38

A maximum tolerated dose of G1T38 has not been established.

There is no specific treatment in the event of G1T38 overdose, and symptoms of overdose are not established. In the event of an overdose, physicians should follow general supportive measures and should treat symptomatically.

Osimertinib

A maximum tolerated dose has not been established for osimertinib.

Such overdoses should be recorded as follows:

- An overdose with associated AEs is recorded as the AE diagnosis/symptoms on the relevant AE modules in the eCRF and on the Overdose eCRF module
- An overdose without associated symptoms is only reported on the Overdose eCRF module

There is no specific treatment in the event of osimertinib overdose, and symptoms of overdose are not established. In the event of an overdose, physicians should follow general supportive measures and should treat symptomatically.

10.6.1.13. Reporting of Pregnancies

Pregnancy is not considered an AE unless there is cause to believe that the investigational drug may have interfered with the effectiveness of a contraceptive medication. Congenital abnormalities/birth defects and spontaneous miscarriages should be reported and handled as SAEs. Elective abortions without complications should not be handled as AEs. Hospitalization for normal delivery of a healthy newborn should not be considered a SAE.

Each pregnancy, including ectopic pregnancy, which occurs during the course of the study and within 6 weeks of the last dose of study drug, in a study patient or partner of a study patient must be reported to the safety team within 24 hours of learning of its occurrence. If a patient becomes pregnant, all study drug administration must be discontinued immediately. The pregnancy should be followed up to determine outcome, including spontaneous or

voluntary termination, details of the birth, and the presence or absence of any birth defects, congenital abnormalities, or maternal and/or newborn complications and documented, even if the subject was discontinued from the study.

The avoidance of pregnancy or fathering a child (including sperm donation) is recommended for 4 months following the discontinuation of study drug. Pregnancy of the subject's partner is not considered to be an AE. No information is currently available regarding the effects of G1T38 on fertility, gestation, or subsequent child development.

To capture information about a pregnancy from the partner of a male subject, the male subject's partner consent must be obtained to collect information related to the pregnancy and outcome; the male subject should not be asked to provide this information. A consent form specific to this situation must be used. The outcome of any conception occurring from the date of the first dose until 4 months after dosing ends should be followed up and documented.

10.6.2. Clinical Laboratory Assessments

Blood samples will be collected for clinical laboratory assessments as outlined in Table 9-1 (Part 1) and Table 9-2 (Part 2). Hematology, clinical chemistry, and urinalysis samples may be obtained up to 48 hours prior to the scheduled visit. If screening hematology, clinical chemistry, and urinalysis assessments have been performed within 7 days of Cycle 1 Day -16 for Part 1 or within 7 days of Cycle 1 Day 1 for Part 2, then these tests do not have to be repeated prior to commencing first treatment with study drug as long as the patient's clinical condition has not changed. After baseline assessment (Day -16 in Part 1, Cycle 1 Day 1 in Part 2), Cystatin C shall be evaluated only in the event that the serum creatinine is elevated. The measurement of Cystatin C to estimate glomerular filtration rate is included in this study because G1T38 may inhibit MATE transporters in the renal tubule and induce a nonpathologic increase in serum creatinine. The clearance of Cystatin C is not dependent upon the MATE transporters and thus can help differentiate the effect of G1T38 on the MATE transporter from a true decline in renal function.

Absolute neutrophil counts will be monitored weekly for the first 8 weeks (2 cycles), then every 2 weeks for the next 2 cycles. Beginning with Cycle 5 Day 1, patients with stable ≤ Grade 2 hematologic parameters may have hematology monitored monthly on Day 1 of each cycle; patients that do not meet this criteria will continue to have every other week assessment of hematologic parameters.

Clinical chemistry will be monitored every 2 weeks for the first 4 cycles. Beginning with Cycle 5 Day 1, clinical chemistry will be monitored monthly on Day 1 of each cycle.

Clinical laboratory tests to be performed are presented in Table 10-5.

Table 10-5 Clinical Laboratory Tests

Hematology Hemoglobin Hematocrit WBCs with differential Platelets	Chemistry Albumin Alkaline phosphatase Total bilirubin Calcium Chloride Creatinine Glucose Inorganic phosphorus	Potassium Total protein ALT AST Lactate dehydrogenase Sodium Blood urea nitrogen/urea Cystatin C ^a
Urinalysis Specific gravity pH Glucose Protein Bilirubin Ketones Leukocytes Hemoglobin Microscopic examination (including RBC, WBC, and casts will be performed, if necessary)	Pregnancy test Blood or urine tests are acceptable based on the site's standard clinical practice; applicable to women of childbearing potential only.	

ALT = alanine aminotransferase; AST = aspartate aminotransferase; RBC = red blood cell; WBC = white blood cell

If treatment is interrupted, the patient should still complete all clinical laboratory assessments as scheduled, as well as on the actual dosing day when treatment is reinitiated.

Laboratory parameters shall be analyzed by a local certified laboratory and a report of the laboratory values shall be sent to the study center. The investigator shall review the laboratory report promptly after receipt of the results and indicate the clinical significance of all abnormal values, and subsequently sign and maintain the laboratory report with the patient's source records/charts. Laboratory parameters for which clinically significant values are noted shall be re-measured on the appropriate clinical follow-up arranged by the investigator. Any laboratory value that remains abnormal at the end of the study and that is considered clinically significant shall be followed according to accepted medical standards for up to 30 days or until resolution of the abnormality, or it is deemed that recovery is not feasible.

Laboratory toxicities shall be assessed using the NCI CTCAE, Version 4.03 (see Appendix 1).

Laboratory abnormalities (eg, clinical chemistry, hematology, and urinalysis) that are associated with signs and/or symptoms must be recorded as an AE or SAE if they meet the definition of an AE or SAE as described in Section 10.6.1.

The SMC/IDMC may modify the frequency of laboratory monitoring based on cumulative safety data.

a Postbaseline Cystatin C to be evaluated in the event that serum creatinine is elevated

10.6.3. Demographics and Vital Signs

The following will be collected at the time points outlined in Table 9-1 (Part 1) and Table 9-2 (Part 2):

- 1. Height in centimeters (cm)
- 2. Body weight in kilogram (kg)
- 3. Body temperature (Celsius)
- 4. Systolic and diastolic blood pressure, pulse rate, and respiration rate; blood pressure should be assessed after 5 minutes of rest and should be assessed predose

10.6.4. Physical Examination

Physical examinations will be performed at the time points outlined in Table 9-1 (Part 1) and Table 9-2 (Part 2).

Full physical examination evaluations at screening and the Post-Treatment visit shall include general appearance, skin, neck, eyes, ears, nose, throat, lungs/respiratory, heart/cardiovascular, abdomen, back, lymph nodes, thyroid, musculoskeletal (including spine and extremities), and neurological examinations. Subsequent physical exams shall be symptom directed and include body systems as appropriate.

Clinically significant findings on physical examination prior to administration of the first dose of study drug must be recorded as medical history in the eCRF. Clinically significant findings on physical examination made after the first dose of study drug, which meet the definition of an AE, must be recorded as an AE in the eCRF.

10.6.5. Electrocardiogram Assessments

All patients will have three 12-lead ECGs performed at the visits indicated in Table 9-1 (Part 1) and Table 9-2 (Part 2).

Part 1 ECG requirements are as follows:

Cycle and Day	Time Points
Screening	Anytime during visit (one set of 3 ECGs)
Cycle 1 Day -16	Predose and at 2 and 6 hours (± 15 minutes) after the G1T38 dose
Cycle 1 Day -2	Predose and at 2 and 6 hours (± 15 minutes) after the G1T38 dose
Cycle 2 Day 1 and Day 1 of each cycle thereafter	Anytime during visit (one set of 3 ECGs)

Patients enrolled in Part 2 of the study will have three 12-lead ECGs performed at screening and Day 1 of each cycle.

A 12-lead ECG will be obtained after the patient has been resting semi-supine for at least 10 minutes prior to times indicated and should be recorded at 25 mm/sec. All ECGs shall be recorded with the patient in the same physical position. The three ECG recordings shall be taken within an approximate 5 minute period. A standardized ECG machine shall be used

and the patient shall be examined using the same ECG machine throughout the study if possible.

After paper ECGs have been recorded, the investigator or designated physician will review each of the ECGs and may refer to a local cardiologist if appropriate. A paper copy should be filed in the patient's medical records. If an abnormal ECG finding at screening or baseline is considered to be clinically significant by the investigator, it must be reported as a concurrent condition. For all ECGs, details of rhythm, ECG intervals, and an overall evaluation will be recorded.

ECG data shall be collected digitally and shall be transferred electronically for central analysis. The investigator may choose to perform a nondigital ECG at the time of the screening visit in order to identify patients eligible for study entry. If a nondigital ECG is performed at the screening visit it cannot subsequently be used as a baseline recording, in this situation an ECG will need to be collected on the baseline visit in digital form.

Heart rate, PR, R-R, QRS, and QT intervals will be determined and reviewed during central analysis by an external cardiologist.

If there is a clinically significant abnormal ECG finding during the Treatment Phase, this should be recorded on the AE eCRF, according to standard AEs collection and reporting processes. A 30-day follow-up assessment will be required if an on treatment assessment was abnormal at the time of discontinuation of study therapy, to confirm reversibility of the abnormality.

The investigator or designee shall review the ECGs for any abnormalities as compared with the baseline ECGs.

10.6.6. Ophthalmic Examination

Full ophthalmic assessment, including slit-lamp examination, shall be performed at screening and if a patient experiences any visual symptoms (including blurring of vision), with additional tests if clinically indicated (Table 9-1 [Part 1] and Table 9-2 [Part 2]). Ophthalmology examination results shall be recorded in the eCRF.

Any clinically significant findings, including those confirmed by the ophthalmologist must be reported as an AE. Photographs should be performed to record any clinically significant findings. These photographs should be available for central review by the sponsor and sponsor representatives if necessary.

Patients experiencing corneal ulceration will not be permitted to restart study treatment.

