8.3.3.2. Osimertinib

Dose modifications for osimertinib for adverse reactions are to be made according to Table 8-2.

If a patient experiences a Grade 3 (CTCAE) or higher and/or unacceptable toxicity (any grade), where the investigator considers the AE of concern to be specifically associated with osimertinib (and not attributable to the disease or disease-related processes for which the patient is being treated), dosing will be interrupted and supportive therapy administered as required in accordance with local practice/guidelines.

If a toxicity resolves or reverts to \leq Grade 2 (CTCAE) within 3 weeks of onset, treatment with osimertinib may be restarted at the same dose or a lower dose using the rules below for dose modifications (Table 8-2) and with discussion and agreement with the sponsor's study team physician as needed. There will be no individual modifications to dosing schedule in response to toxicity, only potential dose reduction or dose interruption.

If the toxicity does not resolve to \leq Grade 2 (CTCAE) after 3 weeks, then osimertinib therapy shall be permanently discontinued and the patient shall be observed until resolution or stabilization of the toxicity.

Patients experiencing any of the following AEs will not be permitted to restart osimertinib treatment:

- Corneal ulceration
- Interstitial lung disease (ILD)
- QTc interval prolongation with signs/symptoms of serious arrhythmia
- Symptomatic congestive heart failure or asymptomatic left ventricular dysfunction that persists ≥ 4 weeks
- Liver function test abnormalities meeting Hy's Law criteria (AST or ALT \geq 3 × ULN and total bilirubin \geq 2 × ULN). All study drugs must be permanently discontinued in any patient meeting Hy's Law criteria.

Table 8-2 Recommended Dose Modifications for Osimertinib-Related Adverse Reactions

Target Organ	Adverse Reaction ^a	Dose Modification
Pulmonary	Interstitial lung disease/ pneumonitis	Permanently discontinue osimertinib
Cardiac	QTc interval > 500 msec on at least	Withhold osimertinib until QTc interval is
	2 separate ECGs	< 481 msec or recovery to baseline, then resume
		at 40 mg dose
	QTc interval prolongation with	Permanently discontinue osimertinib
	signs/symptoms of life-threatening	
	arrhythmia	
	Symptomatic congestive heart failure	Permanently discontinue osimertinib
	or asymptomatic left ventricular	
	dysfunction that persists ≥ 4 weeks	
Other	≥ Grade 3 adverse reaction	Withhold osimertinib for up to 3 weeks

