	If improvement to Grade 0 to 2 within	Resume at 80 or 40 mg daily (investigator's
	3 weeks	discretion)
	If no improvement within 3 weeks	Permanently discontinue osimertinib

ECG = electrocardiogram; QTc = QT interval corrected for heart rate

Source: Table copied from Table 1 of the osimertinib package insert (see Appendix 2)

In the event that the patient experiences a drug-related hematologic toxicity, which may be related to G1T38 or osimertinib, the investigator shall dose-reduce G1T38 first (refer to Section 8.3.3.1).

In the event that the patient receiving G1T38 + osimertinib experiences an osimertinib-related toxicity requiring permanent discontinuation of osimertinib, the patient may continue G1T38 monotherapy at the discretion of the investigator.

a Adverse reactions graded by the National Cancer Institute Common Terminology Criteria for Adverse Events, Version 4.03.

Details regarding the management of specific AEs related to osimertinib are discussed in Sections 8.3.3.2.1 to 8.3.3.2.6.

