8.3.3.2.4. Changes in Cardiac Contractility

Across clinical trials, LVEF decreases of $\geq 10\%$ and a drop to < 50% occurred in 4.0% (26/655) of patients treated with osimertinib who had baseline and at least 1 follow-up LVEF assessment. Based on the available clinical trial data, a causal relationship between effects on changes in cardiac contractility and osimertinib has not been established. In patients with symptomatic congestive heart failure or asymptomatic left ventricular dysfunction that persists ≥ 4 weeks, permanently discontinue osimertinib therapy (Table 8-2).

Permanent Discontinuation Due to Toxicity

Patients experiencing corneal ulceration, ILD, symptomatic congestive heart failure or asymptomatic left ventricular dysfunction that persists ≥ 4 weeks, or QTc prolongation with signs/symptoms of serious arrhythmia will not be permitted to restart osimertinib treatment. Any patient with liver function test abnormalities meeting Hy's Law criteria (AST or ALT $\geq 3 \times \text{ULN}$) and total bilirubin $\geq 2 \times \text{ULN}$) must have all study drugs permanently discontinued.

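### The protocol's stopping rules disagree on whether G1T38 may continue after corneal ulceration, and on when osimertinib's 3-week recovery period starts

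*Protocol*

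**What the plan says.** **Corneal ulceration.** Protocol 8.3.3.2 introduces a list headed by this event with the words "Patients experiencing any of the following AEs will not be permitted to restart osimertinib treatment". The closing paragraph of 8.3.3.2.4 repeats the bar, again for osimertinib: "Patients experiencing corneal ulceration, ILD, symptomatic congestive heart failure or asymptomatic left ventricular dysfunction that persists" and so on. After Table 8-2, section 8.3.3.2 adds that if an osimertinib-related toxicity requires permanent discontinuation of osimertinib in a patient on the combination, "the patient may continue G1T38 monotherapy at the discretion of the investigator". Section 10.6.6 is worded differently: "Patients experiencing corneal ulceration will not be permitted to restart study treatment".

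**Status of Table 8-2.** Section 8.3.3.2 opens with "Dose modifications for osimertinib for adverse reactions are to be made according to Table 8-2". The table has rows for interstitial lung disease, QTc prolongation, cardiac dysfunction and a generic Grade 3 or higher reaction. It has none for corneal ulceration.

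**Recovery period.** For toxicity that resolves to Grade 2 or lower, the 8.3.3.2 text sets the condition as "within 3 weeks of onset, treatment with osimertinib may be restarted". The generic row of Table 8-2 instead says "Withhold osimertinib for up to 3 weeks", then allows resumption on improvement within 3 weeks and requires permanent discontinuation otherwise. A further sentence in the text requires permanent discontinuation if there is no such resolution after 3 weeks, without saying from when.

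**Scope.** The SAP Introduction says Part 2 will not be conducted, so these rules matter for Part 1. From Cycle 1 Day 1 every Part 1 patient is scheduled to take both drugs (Protocol 8.1). The SAP does not address these rules.

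**The concern.** Two sites following the protocol carefully could treat the same patient differently. After an osimertinib-related corneal ulceration, one could keep the patient on G1T38 under 8.3.3.2, while another could stop both drugs under 10.6.6. After another Grade 3 osimertinib reaction, a restart could be allowed under Table 8-2 and yet fail the condition in the text above it.

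Safety and tolerability of the combination is a primary objective of Part 1 (SAP 2.1). SAP 5.2.10 tabulates treatment-emergent events leading to discontinuation of G1T38, of osimertinib and of both, so the reading a site adopts decides the row its patient enters. SAP 5.2.2 classifies protocol deviations as major or minor, and the same restart could be compliant under one passage and a deviation under another.

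**Working it through.** There is no stated figure to reproduce. The check sets the passages side by side and then counts days.

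**1. Which drug is barred after corneal ulceration**

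| Place in protocol | Osimertinib | G1T38 |
|---|---|---|
| 8.3.3.2 list | no restart | not mentioned |
| 8.3.3.2.4, closing paragraph | no restart | not mentioned |
| 8.3.3.2, after Table 8-2 | permanently stopped (the premise) | may continue, if the toxicity is osimertinib-related |
| 10.6.6 | no restart | no restart on the plain reading |
| Table 8-2 | event not listed | outside the table |

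The osimertinib column is consistent wherever the event is named. The G1T38 column is not.

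The term in 10.6.6 is not defined, and its use elsewhere does not settle the matter. Section 8.3.3.2.2 uses it beside a restart of osimertinib alone. Section 9.4 uses it for whatever regimen a patient is still receiving. Where the Hy's Law rule means both drugs, it says so by referring to all study drugs.

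**2. The 3-week recovery period**

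Inputs:
- the limit is 3 weeks = 21 days (8.3.3.2 text and Table 8-2);
- L = days from onset to the first withheld dose. The documents do not give L; I assume 0 to 14;
- R = days from onset to recovery to Grade 2 or lower.

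Conditions for restart:
- text, counted from onset: R ≤ 21;
- table, read as counted from withholding: R − L ≤ 21, that is R ≤ 21 + L.

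The two disagree when 21 < R ≤ 21 + L, which is recovery on days 22 to 21 + L, a span of L days.

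| L (assumed) | Last recovery day allowed, text | Last recovery day allowed, table | Days in conflict |
|---|---|---|---|
| 0 | 21 | 21 | none |
| 5 | 21 | 21 + 5 = 26 | 22-26 |
| 14 | 21 | 21 + 14 = 35 | 22-35 |

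Example: the drug is held 5 days after onset and the event recovers 23 days after onset. From onset, 23 > 21, so the text's condition fails. From withholding, 23 − 5 = 18 ≤ 21, so the table's condition is met.

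The stop sentence does not resolve this. Counted from onset, it requires this patient to stop permanently. Counted from withholding, it does not, but the restart condition in the text is still unmet.

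**3. How often**

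The protocol gives no rate for corneal ulceration. The nearest figure is keratitis, 6/833 = 0.7% (8.3.3.2.3). If that rate applied to the Part 1 maximum of 36 patients, 36 × 6/833 ≈ 0.26 keratitis cases would be expected. Keratitis is not the same event as corneal ulceration, so this indicates rarity only. The recovery-period conflict does not depend on that rate: it covers any Grade 3 or higher osimertinib reaction that falls in the generic row.

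**The case against.** **Table 8-2 does not permit restart after corneal ulceration.** A reader might infer that the generic row allows osimertinib to resume on recovery, giving three outcomes for one patient and possible re-exposure. The documents do not support this. An explicit bar stands in the same section, just above the table, and is repeated in 8.3.3.2.4. The table is titled as recommended modifications and is copied from the package insert, and the text sends the reader to later subsections for specific events. It has no Hy's Law row either, yet restart after such a case is plainly barred. This objection stands: the missing row is an omission to repair.

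**Stopping both drugs is only one reading of 10.6.6.** The use in 8.3.3.2.2 supports a narrower one. Continuing G1T38 is also optional, so a site that stops both drugs breaches nothing. That stands as far as it goes, but a site that continues G1T38 breaches 10.6.6 on its plain reading, and nothing tells it otherwise.

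**The lag may be short.** Dosing is to be interrupted at Grade 3, visits are weekly in Cycles 1 and 2, unscheduled visits are allowed, and restart involves agreement with the sponsor's physician as needed. With no lag there is no conflict. This limits the size. It does not remove the conflict, because scheduled visits become two-weekly in Cycles 3 and 4 and can be four-weekly from Cycle 5.

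**Effects on the analysis could be overread.** A reader might infer that these rules shift the treatment-emergent window or PFS censoring. The window in SAP 4.2.1 follows the later of the two last doses, so stopping osimertinib alone does not set it while G1T38 continues. SAP Table 5-1 does not say whether stopping one of two drugs is treatment discontinuation. Neither consequence is relied on here.

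**Conclusion.** The passages are wrong as written on two points.

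First, after an osimertinib-related corneal ulceration, 8.3.3.2 allows G1T38 to continue, while 10.6.6, read plainly, does not. Osimertinib itself is not in dispute. The event is probably rare.

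Second, the 3-week period for osimertinib starts at onset in the 8.3.3.2 text, reads as starting at withholding in Table 8-2, and has no stated start in the stop sentence. The rules disagree over L days of recovery time: none if the drug is held on the day of onset, and days 22-35 at an assumed lag of 14 days. Section 10.6.6 has no recovery period, so this second conflict concerns restarting or stopping osimertinib and cannot by itself lead to both drugs being stopped.

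The consequences are limited to Part 1, which is descriptive, has no formal test and has at most 36 patients (SAP 2.3 and 5.1.1). They are whether a patient permanently stops a drug, how that discontinuation is tabulated, and whether a restart is a deviation. No power, sample size or error rate is affected. The conclusion rests on the plain meaning of an undefined term, on reading the table's 3 weeks as running from withholding, and on an assumed range for L.

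**What to change.** Reconcile 8.3.3.2, 8.3.3.2.4, Table 8-2 and 10.6.6:

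- state in 10.6.6 which drug or drugs may not be restarted after corneal ulceration, consistently with the G1T38 monotherapy sentence in 8.3.3.2;
- align Table 8-2 with the no-restart list in 8.3.3.2;
- give the 3-week period one start point, and use it in the restart sentence, the stop sentence and the table.

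The choice of rule belongs to the sponsor's clinical team; this point takes no view on it.

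The cost is wording in an amendment or clarification letter, with no added procedures or patients. If dosing has ended, the clinical study report should say which reading sites applied, so that the discontinuation tables and deviation classifications can be interpreted.
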